##### 6.4.3.2 Physician and Patient global assessment for overall disease

The Physician Global Assessment employs a 0-10 Likert scale to assess the patient’s “overall health” in the past 1 week. The single-item question is anchored from 0 (excellent health) to 10 (extremely poor). Using a similar approach, the Patient Global Assessment employs a 0-10 Likert scale for the patient to assess their overall health in the past 1 week. The single-item question is anchored from 0 (excellent health) to 10 (extremely poor).

##### 6.4.3.3 Physician and Patient global assessment for overall disease follow up

In addition to 6.4.3.2, physician assesses changes in the patient’s overall health and lung involvement by transition questions: Compared to the baseline visit, how would you rate your patient’s i) overall health and ii) overall lung involvement. The scale ranges from 1=much better to 5=much worse. Using a similar approach, patient assesses changes in their overall health and lung involvement by transition questions: Compared to your baseline visit, how would you rate your i) overall health and ii) overall lung involvement. The scale ranges from 1=much better to 5=much worse.

##### 6.4.3.4 Leicester Cough Questionnaire (LCQ)

Each question has a score from 1 (severe impact of cough) to 7 (no impact of cough). The total score is the average of three domains: physical, psychological, and social. Total score ranges from 3 to 21. Physical domain will tolerate a maximum of 4 missed items; psychological domain will tolerate maximum of 3 missed items; and social domain will tolerate a maximum of 2 missed items. Higher LCQ score indicates less impact of cough. Three supplement questions after the LCQ questionnaire assess cough severity (0=No cough to 3=Severe), cough frequency (1=Infrequent to 3=Persistent), and phlegm production (1=None to 3=Frequent) in past two weeks.

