- a) St. George's Respiratory Questionnaire (SGRQ): SGRQ, a respiratory disease-specific HRQOL instrument that was originally developed for use in chronic obstructive pulmonary disease, has more recently been used in interstitial lung disease. It will be self-administered at baseline and every 3 months thereafter. This instrument, although not specifically designed for SSc, has recently been validated in SSc-ILD (5). It has been shown to be correlated inversely with FVC and directly with HRCT and exercise performance and to perform better in relation to exercise capacity and lung imaging than other non-respiratory-specific questionnaires for the evaluation of HRQoL in SSc-ILD.

- b) Health assessment questionnaire modified for scleroderma (SHAQ): The SHAQ will be administered at baseline and every 6 months thereafter. The SHAQ was shown to be favorably responsive to CYC therapy in SLS I (26).
- c) Patient-reported outcomes measurement information system 29-item health profile (PROMIS-29). The National Institutes of Health Patient-Reported Outcomes Measurement Information System (PROMIS) roadmap initiative utilized a cooperative group approach to develop and standardize item banks to measure patient-reported outcomes relevant across medical conditions. The resulting PROMIS-29 instrument provides assessment scales for Physical Functioning, Anxiety, Depression, Fatigue, Pain Interference, Sleep Disturbance and Impact on Social Roles, and has been validated to measure health status outcomes in patients with SSc while requiring limited time to repeat (average <2 min) (18). It will be administered at baseline and every 6 months thereafter.
- d) UCLA Scleroderma Clinical Trial Consortium GIT 2.0. The UCLA SCTC GIT is a validated 36-item, self-reported measure assessing bowel involvement, symptoms and related emotional well-being, and social functioning administered at baseline, 6 months, 12 months, 18 months (23-24). A modified version, including only questions #1-8, will be used at screening to determine study eligibility as related to the extent of GI symptoms.
- e) Leicester Cough Questionnaire (LCQ): This self-administered 19-item questionnaire for the quantitative assessment of symptoms of cough frequency and severity will be completed at baseline and every 6 months (30). This will be supplemented with a ranking of cough severity, frequency, and sputum production using a simple likert scale (42,53).

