### 9.3 Demographic and Baseline Variables

Demographic and baseline variables for participants include: age in years at consent, dichotomized age (18-35 years, >35-55 years, >55-75 years, >75 years), sex (Male/Female), ethnicity (Hispanic or Latino/not Hispanic or Latino), race (White/Black or African American/Asian/American Indian or Alaskan native/native Hawaiian or other Pacific Islander), % predicted FVC, FVC (ml), % predicted DLCO (corrected for hemoglobin), time from first non-Raynaud manifestation of SSc in months at screening, modified Rodnan Skin Score (mRSS), Scleroderma classification, Mahler Baseline Dyspnea Index (BDI), St. George's Respiratory Questionnaire (SGRQ) – total and each domain score, Scleroderma Scleroderma Health Assessment Questionnaire (SHAQ), including HAD-DI without Aids/Devices and SHAQ-DI VAS domains, Leicester Cough Questionnaire (LCQ) – total and three supplemental questions, PROMIS-29 domains, UCLA SCTC GIT, physician global assessment, patient global assessment, height, weight, HRCT at screening – quantitative lung fibrosis score in the whole lung (QLF-LM), quantitative lung fibrosis score in the lobe of maximal involvement (QLF-WL), quantitative interstitial lung disease score in the whole lung (QILD-LM), quantitative interstitial lung disease score in the lobe of maximal involvement (QILD-WL), and total lung capacity at maximum inspiration (HRCT-TLC), and laboratory data at screening – sodium, potassium, chloride, CO2, BUN, creatinine, glucose, protein, albumin, bilirubin, alkaline phosphate, AST, ALT, cholesterol, WBC, hemoglobin, hematocrit, platelets, neutrophil percent, absolute neutrophil count, lymphocyte percent, absolute lymphocyte count.

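### The SAP defines the Leicester Cough Questionnaire total as an average of three domains but gives it a 3 to 21 range, which fits their sum; only a descriptive baseline row is affected

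*SAP*

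**What the plan says.** SAP 6.4.3.4 gives the item scale as "Each question has a score from 1 (severe impact of cough) to 7 (no impact of cough"), with higher scores meaning less impact. It then defines the total and, in the next sentence, gives its limits: "The total score is the average of three domains: physical, psychological, and social. Total score ranges from 3 to 21".

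The only other domain-level text concerns missing answers: "Physical domain will tolerate a maximum of 4 missed items; psychological domain will tolerate maximum of 3 missed items", and the social domain tolerates 2. No formula for a domain score is given.

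Protocol 7.1.1.8(e) describes the instrument as "This self-administered 19-item questionnaire for the quantitative assessment of symptoms of cough frequency and severity" and gives no scoring rule. The total is planned for reporting in SAP 9.3, which lists "Leicester Cough Questionnaire (LCQ) – total and three supplemental questions" among the baseline variables.

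**The concern.** An average of three numbers cannot lie outside the range those numbers share. If the domains are on the item scale of 1 to 7, their average is too, and it cannot reach 21. The stated rule and the stated range therefore seem to describe two different scores.

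What is at stake is the scale of one reported variable. A baseline LCQ total computed by the rule could appear beside a 3 to 21 scale to which it does not belong. It could then not be set against other cough data reported on that scale.

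**Working it through.** **Inputs**
- Item score: 1 to 7 (SAP 6.4.3.4).
- Number of domains: 3 (SAP 6.4.3.4).
- Number of items: 19 (Protocol 7.1.1.8(e)).
- Stated range of the total: 3 to 21 (SAP 6.4.3.4).
- How a domain score is formed: not stated, so both usual choices are tried.

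**Can the stated range be reproduced by averaging?**

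| Domain score | Total score | Minimum | Maximum | Gives 3 to 21? |
|---|---|---|---|---|
| Mean of its items | Average of 3 domains | (1+1+1)/3 = 1 | (7+7+7)/3 = 7 | No |
| Sum of its items | Average of 3 domains | 19 × 1/3 = 6.33 | 19 × 7/3 = 44.33 | No |
| Not used | Mean of all 19 items | 1 | 7 | No |
| Not used | Sum of all 19 items | 19 | 133 | No |
| Mean of its items | Sum of 3 domains | 3 × 1 = 3 | 3 × 7 = 21 | **Yes** |

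The second row does not depend on how the 19 items are split between domains, because the three domain sums always add up to the sum of all items.

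**What would make the average of domain sums fit?** With n items in total, the range is n × 1/3 to n × 7/3. Setting n/3 = 3 gives n = 9, and setting 7n/3 = 21 also gives n = 9. The protocol states 19, so this does not rescue the rule.

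**Size, if domains are item means.** Take a patient with domain means of 5, 5 and 5.
- Sum of domains: 5 + 5 + 5 = 15.
- Average of domains: 15/3 = 5.
- Position of 15 on the 3 to 21 scale: (15 − 3)/(21 − 3) = 12/18 = 0.67 of the way to no impact.
- Position of 5 if placed on that same scale: (5 − 3)/18 = 2/18 = 0.11.

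The ratio of the two totals is 3 for every patient.

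**Where the total is used.** The LCQ endpoint in SAP 5.2.3 item 7, and its analysis in SAP 12 item 7, cover only the three supplemental questions on cough severity, cough frequency and phlegm. Protocol 4.2.3.3 lists the LCQ as an endpoint, and SAP 14(c) records its replacement by those questions. The covariates named in SAP 10 do not include the LCQ. That leaves the baseline summary in SAP 9.3, and Protocol 10.4.6 rules out statistical tests between the arms there.

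**The case against.** The strongest reply is that this is one misplaced word with almost no consequence, and much of that stands.

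- **The factor of 3 is conditional.** A reader might infer that the written rule necessarily gives one third of the correct value. The documents do not support that, because the SAP omits the domain step. With domain sums the average runs from 6.33 to 44.33, which is not one third of a 3 to 21 score. Domain means are the more natural reading: the SAP tolerates missed items without giving a proration rule, and a mean of answered items stays on the 1 to 7 scale. This remains an inference.
- **The correct rule is also an inference.** The questionnaire is in Appendix A and the protocol cites a review of cough measures, but neither is available here. The range points to a sum of domain means, and no section states that rule.
- **The error would be easy to notice.** A reader might infer that the published table would make cough look far more severe than it was. That assumes the programmer follows one word, ignores the range in the next sentence, and nobody checks the output against it. Totals that never exceed 7, or that fall below 3, would stand out.

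None of this reconciles the two sentences. No other section of either document supplies a scoring rule or corrects this one.

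**Conclusion.** The inconsistency is real and follows from the documents' own numbers: with 19 items scored 1 to 7, neither way of averaging three domains gives 3 to 21. The contradiction does not depend on how domains are scored, because domain means and domain sums both miss the range. The factor of 3 does depend on it and applies only if domains are item means.

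The importance is low. A reader might infer that a misscaled LCQ could disturb the efficacy results or the comparison of the arms. It could not: no endpoint, model or test uses the total, and dividing every patient's score by 3 rescales both arms alike, leaving their relative comparison unchanged. What is affected is one descriptive baseline row and whether its values can be read against the 3 to 21 scale. The program itself is not available for review, so whether the reported total would be wrong is unknown.

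**What to change.** Replace the scoring sentence in SAP 6.4.3.4 with one stating that each domain score is the mean of its answered items (1 to 7), subject to the existing limits on missed items, and that the total is the sum of the three domain scores (3 to 21). Confirm this against the instrument's scoring instructions before adopting it. Then check that the program computes the total this way, and that no baseline total falls outside 3 to 21.

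The cost is one sentence and at most one line of code. If the program already adds the domain means, only the sentence changes. No endpoint, analysis set or sample size is touched.

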#### **6.4.3.5 Dosing and Adherence**

The proportion of participants reaching and sustaining the maximum dose, and the time to reach the maximum dose and the time remaining at the maximum dose in each treatment group. The time to reach the maximum dose is defined as from date of first dose to the date of 12 pills/day for MMF (1500 mg) and 9 pills/day for PFD (801 mg) and placebo. If a participant did not achieve the maximum dose, they were not included in the calculation of the time to reach maximum dose.

Adherence per protocol is defined as the number of pills taken divided by the number prescribed per the protocol for the duration of time the participant received study medication. Adherence prescribed by PI is defined as the number of pills taken divided by the number prescribed per site PI (e.g., temporarily holding study medication administration for tolerability) for the duration of time the participant received study medication.

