  - a. Using 4 points increments: worsen (1 to 4,  $\geq 5$ ), no change (=0), improved ( $\leq -13, -12$  to -9, -8 to -5, -4 to -1).
  - b. Improved (< -5), no change (-5 to 5), and decreased (> 5).
9. The proportion of participants in each treatment arm achieving the TDI focal score at month 18 as :
  - a. Improved by 1-3, 4-6 and 7-9 points, no change (0) and worsened by 1-3, 4-6 and 7-9 points.
  - b. Improved (>0), no change, deterioration (<0).
10. Tolerability and toxicity of combined MMF and Plac vs MMF and PFD over the course of the 18-month treatment period.
  - a. The time from start of treatment to withdrawal or removal from active drug therapy for any reason.
  - b. Number of participants with treatment-emergent adverse events related to study medication as assessed by system organ classification using preferred Medical Dictionary for Regulatory Activities (MedDRA) terms.

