## 6 Study Methods

### 6.1 General Study Design and Plan

This study is designed as a phase II multi-center, double-blind, parallel group, randomized and placebo-controlled clinical trial addressing the treatment of patients with active and symptomatic SSc-ILD. Eligibility for the study was assessed during a 3-month screening period. Eligible participants were randomized in a 1:1 assignment to receive either oral MMF and Plac (acting as a control arm) or a combination of oral MMF and oral PFD (acting as an experimental arm), with both regimens administered for 18 months.

MMF was administered orally twice daily with a 4-step titration at monthly intervals to a target dose of 1500 mg twice daily as tolerated. PFD/PBO was administered orally three times daily with a 3-step titration at 2 week intervals to a target dose of 801 mg three times daily as tolerated. Patients could receive ongoing treatment with a maximum tolerated dose for either drug that was less than the target dose according to rules defined by the protocol. MMF is approved for use as an immunosuppressant in solid organ transplantation (cardiac, hepatic and renal) at doses up to 1.5 g twice daily and for the treatment of Lupus nephritis, an autoimmune manifestation of systemic lupus erythematosus, in the dose range of 1 to 3 g daily. PFD is currently approved for the treatment of IPF at a recommended dose of 801 mg (3 capsules of 267 mg each) 3 times daily. They were administered in this study at doses that fall within these FDA-defined dosing ranges but as experimental therapy for SSc-ILD.

A participant was considered to have completed the study if he or she completed all phases of the study including the last visit, or the last scheduled procedure, regardless of the dose of either study drug. Participants were followed in the study even if study drug was prematurely discontinued unless they had withdrawn their consent to do so. End of study was constituted by completion of the entire potential 18 months in all randomized participants.

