### 9.4 Treatment Compliance

Compliance with study medication (MMF and PFD/Plac) is assessed and summarized, including

- the proportion of participants who adhered to study treatment, overall and at each study visit,
- the median duration of adherence to study treatment (defined in section 11.1),
- the proportion of participants reaching maximum dose,
- the proportion of participants who sustain their maximum dose,
- the time to reach the maximum dose, and
- the time remaining at the maximum dose.

These are calculated and summarized overall and by treatment group. The maximum dose is 12 pills/day for MMF (1500 mg) and 9 pills/day for PFD (801 mg)/Plac. The proportion of the maximum dose that the participants reached during study period is summarized overall and by treatment group. Participants were expected to take study medication unless it was permanently discontinued due to an AE. The study medication log (Form 027), adverse event form (Form 044), serious adverse event form (Form 045) and final status form (Form 035) are used to derive the compliance measure.

The proportion of participants who permanently discontinued study medication will be summarized with descriptive statistics, overall and by treatment group. A Kaplan-Meier curve will present the time to permanent discontinuation of study medication by treatment group. A listing of these participants with their reason for permanent discontinuation of study medication will be provided.

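### Time to reach maximum dose is summarised by arm only among those who reached it, so the by-arm times are not a randomised comparison and can understate slower titration

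*SAP*

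**What the plan says.** SAP 6.4.3.5 runs the clock from first dose to the date on which the participant is at 12 pills a day of MMF or 9 a day of PFD or placebo. Those who never get there are dropped: "If a participant did not achieve the maximum dose, they were not included in the calculation of the time to reach maximum dose".

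SAP 9.4 lists the measure among the compliance summaries ("the time to reach the maximum dose, and" time remaining at that dose) and says that they are given overall and by treatment group. The same section also gives:

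- "the proportion of participants reaching maximum dose", and the proportion sustaining it;
- how far participants got: "The proportion of the maximum dose that the participants reached during study period is summarized overall and by treatment group";
- who stopped: "A Kaplan-Meier curve will present the time to permanent discontinuation of study medication by treatment group".

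Not reaching target is allowed by design. SAP 6.1 states: "Patients could receive ongoing treatment with a maximum tolerated dose for either drug that was less than the target dose". The formal tolerability endpoint (SAP 5.2.2, item 10a) is a different quantity: "The time from start of treatment to withdrawal or removal from active drug therapy for any reason".

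**The concern.** Reaching maximum dose happens after randomisation and depends on how well the drug is tolerated. A time computed only in those who succeed therefore compares two selected groups. A participant who settles below target, or stops before reaching it, never contributes a long time. That participant simply leaves the calculation. If this happens more often in one arm, that arm's remaining times look shorter than its real titration experience.

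Tolerability of the combination is the secondary objective (Protocol 3, SAP 5.1.2). A reader who sees similar times to maximum dose in the two arms could conclude that titration went equally well.

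The rule also departs from the SAP's usual practice. For time to a 3% FVC-% improvement (SAP 10.2.2, item 5), participants who never achieve it are kept and censored under Kaplan-Meier. No reason is given for treating maximum dose differently.

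**Working it through.** The documents give no figure for this measure, so there is none to reproduce. The check asks which way the rule can push the comparison.

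**Inputs from the documents**

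- The target thresholds are coherent. MMF: 12 × 250 mg = 3000 mg/day, which is 1500 mg twice daily. PFD: 9 × 267 mg = 2403 mg/day, which is 801 mg three times daily.
- Earliest scheduled maximum dose (Protocol 6.1.4): PFD/placebo 2 × 14 = 28 days; MMF 3 × 28 = 84 days when starting at the first level.
- Share reaching maximum dose in each arm: not given. Everything below that depends on it is an assumption.

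**Illustration for PFD/placebo (all hazards assumed)**

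From day 28, let *a* be the hazard per 28 days of reaching maximum dose, and *b* the hazard of giving up on it for good, by stopping or by settling lower. Then:

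- share reaching = a/(a+b);
- median among reachers = 28 + 28·ln 2/(a+b);
- median in all treated = 28 − [28/(a+b)]·ln[1 − 0.5(a+b)/a], which exists only if more than half reach.

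Placebo, a = 1.0, b = 0.1: share = 1.0/1.1 = 91%; reachers' median = 28 + 28 × 0.693/1.1 = 45.6 days; all-treated median = 28 − (28/1.1)·ln(0.45) = 48.3 days.

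Five versions of a worse-tolerating arm, with differences from placebo to the nearest day:

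| a, b | Share reaching | Median, reachers (difference) | Median, all treated (difference) |
|---|---|---|---|
| 1.0, 0.6 | 62.5% | 40.1 d (−6) | 56.2 d (+8) |
| 0.7, 0.4 | 64% | 45.6 d (0) | 67.2 d (+19) |
| 0.5, 0.4 | 56% | 49.6 d (+4) | 99.6 d (+51) |
| 0.3, 0.2 | 60% | 66.8 d (+21) | 128.3 d (+80) |
| 0.4, 0.5 | 44% | 49.6 d (+4) | not reached |

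In this model the reachers' median depends only on a+b, so a higher rate of giving up shortens it. The worse-tolerating arm looks faster in one case, equal in one and slower in three. In all five, the difference among reachers is smaller than, or opposite to, the all-treated difference.

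**A case where the rule changes nothing**

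Suppose 80% and 94% reach maximum dose (assumption). The all-treated median is then the 0.5/0.80 = 62.5th percentile of reachers in one arm and the 0.5/0.94 = 53rd in the other. If about two-thirds of reachers titrate on schedule (assumption), both kinds of median are about day 28 in both arms.

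**What the companion summaries cover**

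The discontinuation curve and endpoint 10a capture people who stop, but not those who stay on drug below target. The proportion reaching maximum dose, and the share of maximum dose reached, do capture the latter. None of them gives the timing of titration in all treated participants.

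**A further point for MMF**

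Participants continuing pre-study MMF may start above the first level (Protocol 6.1.4.1). With 28 days per step, the earliest scheduled time to maximum is 56, 28 or 0 days when starting at the second, third or fourth level, against 84 from the first. The pooled MMF time therefore mixes different starting points.

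**The case against.** The case against making much of this is substantial, and most of it stands.

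- The measure is descriptive, and the SAP specifies no test for it. The exclusion is stated openly. The proportion reaching maximum dose is reported by arm, and SAP 9 lists n among its descriptive statistics, so the missing share should be visible. The table shells are in a separate document that was not available.
- A reader might infer that the worse-tolerating arm must look as fast as, or faster than, the other. That does not follow. If intolerance mainly delays titration, that arm still looks slower, only by less than it should.
- A reader might take 18.5% versus 5.8% from the IPF trials (Protocol 2.3.1.2.3) as the shares who would never reach target. Those figures are gastrointestinal dose reductions or interruptions, in trials with a mean exposure of 62 weeks. A participant can reach target, reduce later and still count as a reacher. Discontinuation for gastrointestinal events was 2.2% versus 1.0%.
- A reader might assume that those who stop for toxicity are the ones removed. In the SSc-ILD tolerability study (Protocol 2.1.6), every discontinuation came more than 3 weeks after full dose, so such participants would be included here. In its 4-week titration group, 1 of 31 stopped for an adverse event.

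These points limit the size and importance of the problem. They do not make the by-arm times comparable, because the companion summaries show how many are missing without repairing the time itself.

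**Conclusion.** The point holds in a limited form. The by-arm times condition on a post-randomisation outcome and should not be read as a comparison of titration speed between randomised groups. The distortion can shrink, remove or, less commonly in the cases tried, reverse a real difference. Its size cannot be stated from the documents, because the share who never reach target is not given. Under assumed hazards, an 8-day slower all-treated median appears as 6 days faster among reachers. Under other assumptions the two medians agree.

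With 51 participants indexed in the SAP 10.1 model, about 25 per arm, leaving out a few people can move a median. It would be wrong to infer that the trial's tolerability conclusion is compromised: endpoint 10 and the primary analysis do not use this measure. This is a low-cost improvement to a minor summary.

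**What to change.** In SAP 6.4.3.5 and 9.4, replace the exclusion rule with an analysis of all dosed participants (the Safety Population). Show the cumulative incidence of reaching maximum dose by arm, separately for MMF and for PFD/placebo. Treat permanent discontinuation of that drug before maximum dose as a competing event, and censor the rest at their last dosing record. Report the median from the curve where it can be estimated.

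If the present summary is kept, label it *among those who reached maximum dose* and print n reached / n treated beside it in each arm. For MMF, also show it by prior-MMF stratum, because of the different starting levels.

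The cost is one extra figure. The dates come from the medication log that SAP 9.4 already names, so no new data are needed. The drawback is that the median will not be estimable in an arm where fewer than half reach maximum dose; the curve itself would then carry the information.
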